Currently in Cambodia, there is no routine formal training of cleaners. The sporadic training sessions that have been organised are insufficient and suboptimal in quality. To bridge this gap in environmental hygiene training, the National Institute for Public Health (NIPH) together with the Cambodian Ministry of Health's Department of Hospital Services (DHS), and WaterAid Cambodia decided to provide training on environmental hygiene to frontline cleaners from 13 public hospitals in Cambodia using an internationally recognised package of training on environmental hygiene: TEACH CLEAN (<https://www.lshtm.ac.uk/research/centres/march-centre/soapbox-collaborative/teach-clean>) (7). Environmental hygiene training has never been formally evaluated in the low resourced contexts, although pilot evaluation in other contexts show promising results (8). The more recent version is currently being adapted by the WHO for global roll out.

In collaboration with NIPH, DHS, WaterAid, the research team at the London School of Hygiene and Tropical Medicine (LSHTM) aims to thoroughly evaluate this roll out. The study described below represents the first randomised trial in a low-resource setting testing an environmental hygiene education intervention.

2 Objectives

The main objective is to evaluate the effectiveness of an innovative environmental cleaning bundle, TEACH CLEAN, as an intervention to improve microbiological cleanliness in Cambodian hospitals. More specifically, this study aims to:

- Assess whether the quality of microbiological cleanliness (primary outcome) changes as a result of the intervention
- Assess whether in absence/presence of *S. aureus*/MRSA changes as a result of the intervention
- Explore knowledge, self-efficacy and social norms among cleaners and investigate whether they vary by the degree of implementation strength, and possibly by level of microbiological cleanliness

- Explore the association between the degree of implementation strength and microbiological cleanliness

It is expected that an effective and tailor-made environmental cleaning bundle will be taken up and integrated in national training programs and guidelines on environment cleaning and hygiene in healthcare facilities and further scaled up in Cambodia. Ultimately, this will contribute to reducing healthcare associated infections in the country and globally through sharing of such innovative training package.

3 Methods

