3.1 Study design

This is a randomised controlled trial using a stepped-wedge random allocation with the following details:

- The environmental hygiene intervention will be rolled out to thirteen hospitals over ten months
- The main intervention – the training of trainers/champions (ToT) will be delivered to selected cleaning champions from three or four hospitals within a certain month (within the same 4 weeks of a specific month in the schedule), hence there will be a total of 4 steps (4 main periods when training happens)
- **The timing allocation for hospitals matched with the four training periods is random**
- The results across unexposed observation periods are compared with that across the exposed observation period
- The stepped-wedge design, with staggered timings for the start of the intervention and intervention length (2 to 8 months), supports feasibility while maintaining the rigour of the study.
- The design allows the NIPH and its partners to work with a group of hospitals at the time to maximise quality and consistency of the implementation, and avoid having to manage the changes across 13 hospitals simultaneously

This is the suitable design to ensure that all the 13 participating hospitals receive the interventions as proposed by NIPH and its partners whilst keeping the rigor of randomisation based on timing.

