3.4.1 Process evaluation

A process evaluation conducted by the Cambodia WaterAid team together with the LSHTM team will aim to capture information around the following aspects of implementation as recommended by the Medical Research Council (UK) guidelines for process evaluations of complex interventions: implementation fidelity, dose, mechanisms, reach and context:

- **Implementation fidelity** will be measured through semi-structured observations of trainings at the ToT level and facility level – we will aim for at least one set of training to be observed in each facility (N=13-26 trainings observed) and using interviews and focus group discussions (FGDs) with stakeholders by an experienced qualitative researcher (see Appendix 3 and Appendix 4). Phone interviews will be conducted with a sample champions and cleaners at regular intervals across the study to assess both implementation fidelity in terms of supportive supervision and contextual changes described just below (See Appendix 3 and Appendix 4).
- With regards to **context**, we will map the hospital characteristics and context (e.g. staffing, size), infection prevention policies and practices (e.g. antimicrobial stewardship, antibiotic use, screening) and other relevant activities (e.g. cleaning staff changes, policy changes) within the hospital in a qualitative way through stakeholders interviews (see Appendix 3). Ongoing reviews of contextual information throughout the intervention at each site will assist with trial site comparisons, replication and scalability and knowledge translation
- **Dose and reach** of the intervention will also be monitored e.g. number of modules delivered, number of facility staff trained, number of supervision sessions. This information will be collected using training records.
- **Data on mechanisms** (e.g. increase in knowledge) through which the intervention is believed to work will also be collected through a quantitative survey enquiring about knowledge, social norms, network structure and self-efficacy measures. See Appendix 5 for the draft survey. The survey will be administered to all staff who cleans in the selected facilities at the end of the trial will allow us to compare knowledge and attitudes scores between control and intervention clusters. This is particularly important to gauge whether the bundle has impacted not only upon behaviour but also on knowledge, which are the longer-term drivers of behavioural outcomes.

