Power calculations for primary outcome: The intervention will be delivered in four steps across thirteen hospitals (3 hospitals per step; except for one step with 4 hospitals – see Figure 1), with 30 sampling sites each and with a pre-training cleanliness proportion ranging from 30% to 50% will give us over 85% power to detect a 30% relative increase in microbiological cleanliness. This is based on a two-sided 5 % significance level, a two-period decay correlation structure with the following conservative estimates of within- period ICC in microbiological cleanliness at 0.03 (previous pilot), auto-correlation of observation at 0.6 and cluster auto-correlation at 0.6, and the intervention timings shown in Figure 1. The pre- intervention cleanliness proportion, and the within-hospital ICC and were estimated using a pilot data from similar level maternity wards in Tanzania as no local data is available on microbiological cleanliness; other available evidence on levels of microbiological cleanliness confirm in settings with no formal training sow similar levels of hospital cleanliness in low resource settings.(8) We assumed one month delay in the treatment effect for the sample size calculation to allow for champions to train staff in their own facility.

We used the website (<https://clusterrcts.shinyapps.io/rshinyapp/>) and underlying formula operationalised by Hemming et al. (2020).(15) See results in Figure 2.

The power calculations translate **into 4,300 dipslides** (13 hospitals*30 sampling sites*10 months = 3,900 + 10% for contingency purposes)

Figure 2. Sample size calculations

Curve shows the increase in power as the cluster-period size increases (for a fixed number of clusters). Hover cursor over curve to see actual power values

Warning: caution is needed with CRTs with a small number of clusters due to risk of lack of internal and external validity; and appropriateness of calculations used particularly for binary and count outcomes

Parameters:

p0: 0.3 p1: 0.39

Significance level: 0.05

Number clusters per sequence: 1

WP-ICC: 0.03 WP-ICC (lower): 0.01 WP-ICC (upper): 0.05 CAC: 0.602

Individual auto-correlation: 0.6

Data analyses: Aerobic Colony Counts and *S. Aureus* outcomes

- The outcome for unexposed observation periods is compared with that across the exposed observation periods.

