- The key independent variable will be the intervention (yes/no). The intervention variable will switch from “no” to “yes” after the first full month of the training
- Characteristics of the individual sites and clusters will be summarised by exposure status so to allow consideration of selection biases and lack of balance.
- These characteristics can be compared by randomisation step. This will include the numbers analysed, the average cluster size, and cluster characteristics
- A few characteristics of the hospital (e.g. size) will be considered as independent variables as these should remain roughly constant throughout the study.
- Each cluster will be analysed according to the actual time when it was “trained” independently on when this was planned for.
- Calendar time is associated with both the exposure to the intervention and also possibly the outcome, and so is a potential confounder and will be adjusted for in the analysis
- Adjusting for the systematically different observation periods and for clustering in the data will be accomplished.
- We will test the residuals of the model to look for autocorrelation over time and will check for influential observations.
- The estimated intra-cluster correlation and time effect from the fitted model will be reported both for use in the design of future trials and to allow appreciation of any underlying confounding effects of calendar time
- We will consider using a small sample correction.

In addition, using the same general model we will create a variable indicating the strength of implementation which we will use as an alternative exposure variable to the simpler *intervention vs control variable*. We will also explore descriptively time trends for each cluster. Finally, we will analyse the knowledge and attitudes descriptively (and by implementation *strength and by microbiological outcomes*) as these measures are only collected at the end of the trial.

Qualitative data from FGDs and observations will be analysed adopting a generalised qualitative approach in which the transcripts were disassembled into low-level descriptive codes and then reassembled into themes that may help explain the observed outcomes

4 Data and reporting

Please refer to our exhaustive data management plan as in Appendix 7. The Consort 2018 extension to stepped wedge randomised trials will be used (16).

5 Ethical approval and consent

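### Swapping a strength score for the yes/no intervention term would largely re-measure the on/off effect if the score is numeric and near zero before training

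*Combined protocol and SAP*

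**What the plan says.** Protocol section 2 lists as an aim: "Explore the association between the degree of implementation strength and microbiological cleanliness". Section 3.4.2 gives the main exposure: "The key independent variable will be the intervention (yes/no"). The same list sets the change from unexposed to exposed with a lag: "The intervention variable will switch from “no” to “yes” after the first full month of the training". A further analysis then leaves the rest of the model as it is: "we will create a variable indicating the strength of implementation which we will use as an alternative exposure variable to the simpler". That sentence goes on to name the on/off comparison as the variable being replaced.

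The protocol does not give the items, scale or timing of the strength variable, or its value in control months. The nearest candidates are the dose and reach items in section 3.4.1, taken from training records: "number of modules delivered, number of facility staff trained, number of supervision sessions". The protocol does not link these items to the strength variable.

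For strength and cleanliness, neither document describes a joint model, an analysis limited to exposed months, or a comparison of fit between the two exposure codings. The SAP does not mention implementation strength.

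**The concern.** Let X be the yes/no exposure and S the strength score. If S is about zero whenever X = 0 and positive whenever X = 1, then S is largely X rescaled. Once X is removed from the model, any effect of being trained at all has to load onto S. The coefficient is then positive whether better-implementing hospitals become cleaner or all trained hospitals improve equally. Those are the two situations the objective sets out to tell apart.

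A related ambiguity concerns time. Section 3.1 describes a design "with staggered timings for the start of the intervention and intervention length (2 to 8 months"), so the length of exposure is set by sequence. Counts such as supervision sessions or staff trained could grow with months since training. A running total would then partly reflect sequence and time since training. The protocol does not say whether the score accumulates.

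What is at stake is the interpretation of an exploratory result: a coefficient labelled as strength could be read as a dose-response relation when it mostly restates the primary effect.

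**Working it through.** **Inputs from the protocol (3.1 and 3.4.2).** "four steps across thirteen hospitals (3 hospitals per step; except for one step with 4 hospitals"); 10 months; 30 samples per hospital-month; cleanliness 0.30 rising to 0.39; within-period ICC 0.03; cluster autocorrelation 0.602; individual autocorrelation 0.6; two-sided 5%. Exposure of 2 to 8 months is coded as starting in months 3, 5, 7 and 9 (10 − 3 + 1 = 8; 10 − 9 + 1 = 2), with 3, 3, 4 and 3 hospitals.

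**Assumptions.** The documents give no distribution for strength. It is taken as 0 in control months, constant within a hospital once exposed, and drawn uniformly from a to 1, with a = 0.2, 0.4, 0.6 or 0.8 (1,000 draws each).

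**Step 1: reproduce the plan's power.** Generalised least squares (GLS) on hospital-month means, with fixed month effects plus exposure.
- Average binomial variance: (0.30 × 0.70 + 0.39 × 0.61)/2 = 0.22395.
- Covariance between months t and s: 0.22395 × [0.03 × 0.602^|t−s| + (0.97/30) × r], with r = 1 if t = s and 0.6 otherwise.
- The standard error of the on/off effect is 0.0301. Power = Φ(0.09/0.0301 − 1.96) = 0.848, which matches the stated 85%.
- If the individual autocorrelation decays (r = 0.6^|t−s|), power is 0.785.

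**Step 2: the planned substitution.** Fit month effects + βS when the truth is month effects + 0.09X, so that strength is irrelevant once a hospital is trained. Compare this with a truth fully proportional to strength: 0.09 × S divided by the mean strength of the 13 hospitals.

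| Strength range | Correlation of S with X | Mean β, strength irrelevant | Rejects, strength irrelevant | Rejects, effect proportional |
|---|---|---|---|---|
| 0.2–1 | 0.89 | 0.114 | 74% | 93% |
| 0.4–1 | 0.95 | 0.114 | 80% | 89% |
| 0.6–1 | 0.98 | 0.108 | 83% | 86% |
| 0.8–1 | 0.996 | 0.099 | 85% | 85% |

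The true gradient among trained hospitals in the fourth and fifth columns' first case is zero, yet β averages 0.10 to 0.11. The last two columns are close together, so a significant result barely separates the two situations. With decaying individual autocorrelation, the strength-irrelevant rejection rates are 66%, 73%, 77% and 78%.

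**Step 3: an estimator closer to the SAP's.** 1,500 binomial simulations per setting, using a linear GEE with exchangeable working correlation, Kauermann-Carroll correction and t(11), without individual autocorrelation. Irrelevant strength is significant in 46% (0.2–1), 56% (0.4–1) and 65% (0.8–1) of trials. With no effect of any kind, the rates are 8.1%, 6.5% and 5.6%. This is a simplification of the SAP model, which is a logit GEE on single samples with covariates.

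**Step 4: larger effects.** A 30% relative increase on 30% to 50% is 9 to 15 points (0.3 × 0.30 = 0.09; 0.3 × 0.50 = 0.15). In a separate simulation of 600 trials per scenario (SAP Figure 1 timings, strength uniform on 0.5–1, decaying autocorrelation, exchangeable working correlation with a Kauermann-Carroll-type correction), irrelevant strength is significant in 48%, 71% and 88% at 9, 12 and 15 points.

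**Step 5: keep X and add centred strength.** Fit month effects + θX + γX(s − s̄), where s is the hospital's strength and s̄ its mean over the 13 hospitals. When strength is irrelevant, γ rejects in 5.0% of trials by GLS, about 7% in the Step 4 simulation, and 8% to 9% in the Step 3 GEE, where its rate with no effect at all is 8.5% to 9.5%. When the effect is fully proportional to strength, the power for γ by GLS is 40% (0.2–1), 19% (0.4–1), 10% (0.6–1) and 6% (0.8–1).

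**The case against.** The strongest reply is that the problem depends on a coding the protocol never states. The dose and reach items are listed for the process evaluation, not as components of the strength variable. The yes/no variable switches only after a month's lag, so some training may fall in months still coded as control, and a dose score could be positive there. A score built on practices that exist before training need not be zero either. If the variable were categorical (none, low, high), replacing the yes/no term would be sound: an on/off effect would show as equal low and high coefficients. All of this stands, and it is why the point is conditional on a numeric score at or near zero before training.

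A reader might infer that the trial cannot answer whether strength matters. The documents do not support that. The limitation belongs to the planned coefficient; the same data could address the question through a joint model or the exposed months alone. A reader might also infer that scale-up advice would rest on this coefficient. Section 2 ties uptake to an effective bundle, not to a strength gradient, so that harm is speculative. The suggestion that a cumulative score would measure sequence was not simulated; strength was held constant within each hospital.

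Finally, SAP section 4.1 declines to claim significance from a p-value cut-off, and the check is largely in rejection rates. That limits their practical weight. It does not remove the problem, because the estimate itself is displaced: β averages about 0.10 to 0.11 when the gradient among trained hospitals is zero.

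**Conclusion.** The concern holds conditionally. The protocol substitutes strength for the yes/no term, leaves strength undefined, and offers no other analysis of its association with cleanliness. If the score is numeric and at or near zero before training, its coefficient mainly reflects trained versus untrained months. At a pure on/off effect of 9 points it would be nominally significant in roughly 45% to 85% of trials although strength is irrelevant, so a positive result is not evidence of a strength gradient.

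The range reflects assumed strength distributions, two forms of individual autocorrelation, and GLS versus GEE. It does not apply to a categorical score read by its exposed-level contrast. The analysis is exploratory and absent from the SAP, so the primary result is untouched.

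**What to change.** In the SAP, either state that the strength analysis is dropped or specify it as follows.

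- Define the score: its items, scale, timing, and value in control months, including the month between champion training and the switch to exposed.
- Keep the yes/no term and add strength centred among exposed hospital-months. Alternatively, use none/low/high categories and interpret only the contrast among exposed levels.
- Interpret only that added term or contrast as the strength association. Report it with its confidence interval and label it exploratory and non-randomised.
- If any item accumulates, express it per exposed month or account for time since training.

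The cost is a short paragraph in the SAP plus the work of fixing the score definition. The drawback is imprecision: the estimate rests on differences among 13 hospitals, with the low power shown in Step 5, and the small-sample GEE test of the added term runs somewhat above 5%. A null finding could not be read as showing that strength is unimportant.
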